8.1.3 VARIATION FROM SCHEDULED VISIT DAYS

To allow for scheduling flexibility, limited variation will be permitted from the specified time of each visit (Table 3).

Table 3. Allowed Variation from Scheduled Visit Days

Scheduled Visit After Each Treatment	Allowed Variation (calendar days)
Weeks 4 and 6	± 3 days
Weeks 12, 16, 20, 24, 28, 32, 36, 40, 44, 48, and 52/EOS	± 6 days
Treatment #2, #3, and #4	± 14 days

Note: Two weeks after each Treatment (at Week 2 [allowed variation: ± 3 days]), the subject will be contacted by telephone to follow up on clinical effect, any AEs or changes in concomitant medications.

A subject who experiences significant recurrence of CD symptoms (e.g. pain) during the study before his/her TWSTRS-total score reaches the target TWSTRS score may request another treatment before the next scheduled visit. In this case, the subject may have an unscheduled visit for the investigator to assess whether another treatment is warranted based on the subject's symptoms and neurologic exam findings. If the investigator confirms that retreatment is clinically indicated, the subject may receive another treatment at this visit, unless less than 12 weeks have passed since the last injection or the injection will occur after Week 40 (i.e., there is less than 12 weeks of follow up left in the 52-week study period).

Note: After each Treatment, study visits are reset to begin from that Treatment to Week 4, Week 6, Week 12, and every 4 weeks thereafter.

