3.4. Brief Description

This is a Phase 3, open-label, multi-center trial to evaluate the long-term safety, efficacy, and immunogenicity of up to four continuous treatment cycles of DAXI for injection at doses of 125 U, 200 U, 250 U, and 300 U in adults with isolated CD at study centers across the United States, Canada, and Europe.

Approximately 350 adult subjects will be recruited from study centers who were previously enrolled in Protocol 1720302 entitled [A Phase 3, Randomized, Double-Blind, Placebo-Controlled, Parallel Group, Multi-Center Trial to Evaluate the Efficacy and Safety of a Single Treatment of DaxibotulinumtoxinA for Injection in Adults with Isolated Cervical Dystonia (ASPEN-1)]. These subjects will have 7 days from their End-of-Study (EOS) Visit in Protocol 1720302 to decide if they want to enroll in this study. After enrolling, subjects will have up to 21 days to complete screening procedures. After 21 days, subjects who have NOT completed the screening procedures will be considered a screen failure. To be reconsidered for enrollment to this study, the subject will be required to repeat all screening procedures to reconfirm eligibility for enrollment. These criteria also apply to subjects who missed the 7-day decision-making window to enroll in this study. This study will also recruit new botulinum neurotoxin (BoNT) treatment-naïve or -experienced adult subjects who were not enrolled in Protocol 1720302.

[REDACTED]

[REDACTED]

This document is confidential.

[REDACTED]

The primary endpoints are safety and immunogenicity. [REDACTED]

[REDACTED]

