4.1. Primary Endpoints

The primary endpoints of this study are:

- The dose- and cycle-specific incidence of drug-related adverse events (AEs)
- The dose- and cycle-specific incidence of study drug discontinuation due to drug-related AEs
- The dose- and cycle-specific incidence of treatment-emergent immunogenicity

This document is confidential.

5. Analysis Sets

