9.3. Adverse Events

AEs will be coded using MedDRA version 22.0 or later. An AE will be considered treatment emergent if the event begins on or after the date of first dose of study medication or if the event begins before and worsens in severity after the date of first dose of study medication. An adverse event with a relationship to study medication of definite, probable, or possible is also considered to be treatment-emergent.

AEs will be summarized by system organ class (SOC) and preferred term (PT). An AE is considered related to study treatment if the relationship is considered as definite, probable, or possible. If the relationship to study treatment is missing, the AE will be counted as definite in summary tables. If the severity is missing, then the AE will be counted as severe in summary tables. Actual missing values will be presented in the listings.

Summary tables will be provided for treatment-emergent AEs (TEAEs) by dose and treatment cycle and overall for the following:

- Overall summary of TEAEs
- TEAEs by SOC and PT
- TEAEs by PT with a frequency of at least 3% overall
- TEAEs by SOC, PT, and maximum severity
- TEAEs by SOC, PT, and strongest study medication relationship
- Treatment-related TEAEs by SOC and PT
- Serious TEAEs by SOC and PT
- TEAEs resulting in study medication discontinuation by SOC and PT
- TEAEs of special interest by SOC and PT

[REDACTED]

In addition, summaries will be provided by the following dose groups:

- HDHF: High dose, high frequency group, defined as subjects who received a high dose (250 U or 300 U) for 3 or 4 cycles

This document is confidential.

- HDLF: High dose, low frequency group, defined as subjects who received a high dose (250 U or 300 U) for 1 or 2 cycles
- LDHF: Low dose, high frequency group, defined as subjects who received a low dose (125 U or 200U) for 3 or 4 cycles
- LDLF: Low dose, low frequency group, defined as subjects who received a low dose (125 U or 200 U) for 1 or 2 cycles

Subjects will appear in only one group, and TEAEs will be summarized for subjects in each group. Subjects who received a high dose for 2 cycles and a low dose for 2 cycles will be included in the HF group. Subjects who received a high dose for 1 cycle and a low dose for 1 cycle will be included in the HL group.

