The overall summary of TEAEs will include the number and percentage of subjects with a TEAE, with treatment-related TEAEs, with serious TEAEs, treatment-related serious TEAEs, with TEAEs of special interest, [REDACTED], related to anaphylactic reaction, with toxin-related TEAEs, with TEAEs leading to death, and with TEAEs leading to study discontinuation. The number of events will also be provided. For TEAE summaries, the number and percentage of subjects will be presented by SOC and PT by treatment. Subjects will be counted only once for each SOC and for each PT within each SOC. For summaries by maximum severity and strongest relationship, if a subject has the same event more than once, the subject will be included only once at the worst severity or strongest relationship. Summary tables by SOC and PT will be sorted in descending frequency by SOC and then by PT within each SOC by the overall column. All AEs will be included in the listings. Listings will be provided for all AEs, serious AEs, and AEs resulting in study medication discontinuation. All information pertaining to AEs noted during the trial will be listed by subject, detailing the verbatim description given by the Investigator, preferred term, system organ class, start date, stop date, severity, action taken regarding study drug, outcome, and drug relatedness. The event onset will also be shown relative (in number of days) to the date of first dose of study treatment administration. In addition, a list of subjects who prematurely discontinue from the trial due to adverse events will also be provided.

[REDACTED]

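### Crude AE percentages by dose and cycle are not directly comparable, because time at risk differs between cycles and no adjustment is visible

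*SAP*

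**What the plan says.** The first primary endpoint in SAP 4.1 is "The dose- and cycle-specific incidence of drug-related adverse events (AEs". The second has the same form, for study drug discontinuation due to such events. The study covers "up to four continuous treatment cycles of DAXI for injection at doses of 125 U, 200 U, 250 U, and 300 U" (SAP 3.4).

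SAP 9.3 sets the layout: "Summary tables will be provided for treatment-emergent AEs (TEAEs) by dose and treatment cycle and overall". The measure is a count and a percentage: "For TEAE summaries, the number and percentage of subjects will be presented by SOC and PT by treatment". For the overall summary it adds: "The number of events will also be provided". The visible text gives no person-time denominator, per-cycle onset window, time-to-first-event analysis or confidence interval for AEs. Parts of 9.3 are redacted.

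Cycle length is not fixed. Protocol 7.1 makes further treatment depend on the response to the previous one. Protocol 8.1.3 allows retreatment "unless less than 12 weeks have passed since the last injection or the injection will occur after Week 40", and explains the Week 40 limit as the point after which "there is less than 12 weeks of follow up left in the 52-week study period".

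Two other places bear on the point. SAP 7.1 summarises duration of participation, in categories from under 4 weeks to 36 weeks or more, but does not link it to AE incidence. SAP 9.5 bases laboratory shift tables on Week 12 of each cycle, so a common per-cycle cut already exists for another safety measure.

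**The concern.** An endpoint defined by dose and cycle invites two comparisons: later cycles against earlier ones, and one dose against another. A crude percentage supports them only if time at risk is similar. Here a cycle ends when the subject needs retreatment or the study ends, so its length depends on response, on when the cycle started and on the 52-week limit. A difference between two cells of the table could be a difference in risk, in length of observation, or both, and the visible outputs do not let a reader separate them. In a long-term repeat-dose study, whether risk changes with repeated treatment is the main safety question.

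**Working it through.** **1. The plan's timing rule.** 52 − 12 = Week 40 as the last permitted injection, as stated. With a 12-week minimum, the earliest starts are Weeks 0, 12, 24 and 36, so four cycles are the maximum.

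**2. Possible cycle lengths** (subject stays on study; visit windows ignored). The maximum is 52 minus the earliest start; the minimum is 12.

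| Cycle | Earliest start (week) | Possible length (weeks) |
|---|---|---|
| 1 | 0 | 12-52 |
| 2 | 12 | 12-40 |
| 3 | 24 | 12-28 |
| 4 | 36 | 12-16 |

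Subjects can leave before Week 12 (Protocol 7.2 and 8.1.2.4), so 12 is not a true lower bound on follow-up.

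**3. Effect of length alone.** Assume a constant hazard of 0.5% per week in every cycle and dose. Incidence over L weeks is 1 − exp(−0.005 × L): 5.8% at 12 weeks, 7.7% at 16, 13.1% at 28, 18.1% at 40 and 22.9% at 52.

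**4. Direction for single subjects.** Retreated exactly every 12 weeks, a subject has cycles of 12/12/12/16 weeks: 5.8/5.8/5.8/7.7%, so the last is highest. Retreated every 20 weeks, the cycles are 20/20/12 weeks: 9.5/9.5/5.8%, so the last is lowest.

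**5. Populations.** This is a simulation with log-normal retreatment intervals (SD of log 0.25 between and 0.20 within subjects), the 12-week and Week 40 rules, at most four cycles and follow-up to Week 52. The hazard, medians and spreads are all assumptions; the documents give none.

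| Median interval (weeks) | Retreatment times | Cycles 1/2/3/4, crude % |
|---|---|---|
| 14 | continuous | 7.4/7.7/8.2/7.1 |
| 20 | continuous | 10.0/10.2/8.5/6.9 |
| 24 | continuous | 11.9/10.9/8.2/6.7 |
| 14 | 4-weekly visits | 8.1/8.3/7.9/6.8 |
| 20 | 4-weekly visits | 10.9/10.5/7.7/6.4 |
| 24 | 4-weekly visits | 12.8/10.7/7.3/6.3 |

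The lowest cell can be checked by hand: mean cycle 4 length is 13.0 weeks, and 1 − exp(−0.005 × 13.0) = 6.3%. Within 12 weeks, every cell is 1 − exp(−0.06) = 5.8%.

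With continuous times, moving the median from 18 to 24 weeks raises cycle 1 from 9.1% to 11.9% but lowers cycle 3 from 8.6% to 8.2%, because longer early cycles leave less of the 52 weeks. At a median of 20 weeks, about 49% of subjects reach cycle 3 and 5% reach cycle 4.

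**6. If all risk falls in the first 12 weeks.** Every cycle then gives the same crude percentage, apart from early leavers. The exposure-adjusted rate becomes the misleading measure. With a 12-week risk of 20% (assumed), the hazard is −ln(0.8)/12 = 1.86 per 100 subject-weeks. In a 24-week cycle, time to first event or cycle end averages 0.20/0.0186 + 0.80 × 12 = 20.4 weeks, so the rate is 0.20/20.4 = 0.98 per 100. A 12-week incidence is stable under both patterns.

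**The case against.** The strongest reply is that the endpoint concerns drug-related AEs, which may arise soon after injection. The 12-week minimum then gives nearly every cycle the same relevant window, and step 6 shows almost no distortion. This stands as a limit on the size. It does not settle the matter: SAP 9.3 counts possible relationship as related, Protocol 8.3.3.2 lets that category apply without a plausible time sequence, and 9.3 counts a missing relationship as definite. Late events can therefore enter the endpoint. The all-TEAE and serious-TEAE tables are more exposed.

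The study is also descriptive, sized on a regulatory exposure requirement, and tests no hypothesis across cycles. It does report event counts, participation time and groups by dose level and number of cycles. That is fair, and makes this an improvement in interpretability rather than the repair of an invalid test.

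Three stronger readings are tempting and not supported:
- **Incidence must fall from cycle to cycle.** Cycle 4 was below cycle 1 in every simulated population, but cycles 2 or 3 can exceed cycle 1, and the 12-week subject in step 4 shows a rise.
- **A longer-acting dose looks worse.** Longer action raises cycle 1, but can lower cycles 3 and 4. No visible text says that any dose acts longer.
- **The SAP contains no adjustment.** Redacted text in 9.3 could hold an exposure-adjusted table or a rule assigning events to cycles. Only its absence from the public text can be stated.

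**Conclusion.** The point holds in limited form. In the visible text, the primary AE incidences are crude percentages over cycles whose possible lengths differ widely, so they are not directly comparable across cycles or doses. Under the stated assumptions the size is about 6% to 13% across cycles, where a common 12-week window gives 5.8% throughout. Those figures rest on a constant weekly hazard and assumed retreatment intervals; with risk concentrated soon after injection, the distortion is small. Its direction cannot be predicted from the documents beyond a tendency for cycle 4 to lie below cycle 1, so a reader cannot correct for it by eye.

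**What to change.** For the primary AE endpoints, add to SAP 9.3, by dose and cycle:

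- **(a) Measure for comparing cycles and doses:** incidence with onset within 12 weeks of that cycle's injection, with a 95% CI. Estimate it by Kaplan-Meier at Week 12, or state the at-risk denominator, because some subjects leave earlier. This matches the Week 12 cut already used for laboratory shifts.
- **(b) Supplement:** exposure-adjusted rates per 100 subject-years over the full cycle, with total exposure shown for each dose and cycle.

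Keep the crude percentage. Optionally, repeat the across-cycle display in subjects with three or more cycles, since later cycles contain a selected group. If the redacted text already provides (a) or (b), a cross-reference suffices.

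The cost is SAP wording and extra table columns, with no new data. Listings give onset in days from the first dose of study treatment, so onset within a cycle must be derived from AE start and injection dates. The downside is that (a) leaves out later-onset events; the crude percentage and the rate still show them.

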3.6. Determination of Sample Size

The sample size for this study is based on a requirement from Regulatory Authorities to collect safety data on approximately 350 subjects treated once and long-term safety data on at least 100 adult subjects with isolated CD treated with 3 or 4 continuous treatment cycles, of low-dose or high-dose DAXI for injection, with at least 50 subjects treated with the high-dose DAXI for injection for 3 or 4 continuous treatment cycles. [REDACTED]

This document is confidential.

[REDACTED]

[REDACTED]

[REDACTED]

[REDACTED]

[REDACTED]

[REDACTED]

[REDACTED]

[REDACTED]

[figure not shown]
[REDACTED]

[figure not shown]
[REDACTED]

3.9. [REDACTED]

[REDACTED]

This document is confidential.

[figure not shown]

4. Endpoints

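### The four dose-frequency adverse-event groups in SAP 9.3 overlap for every mixed-dose subject, and the tie-breaks neither cover all cases nor name defined groups

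*SAP*

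**What the plan says.** After listing the main treatment-emergent adverse event (TEAE) tables, SAP 9.3 adds summaries for four exposure groups:

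- HDHF (high dose, high frequency): "defined as subjects who received a high dose (250 U or 300 U) for 3 or 4 cycles".
- HDLF (high dose, low frequency): "defined as subjects who received a high dose (250 U or 300 U) for 1 or 2 cycles".
- LDHF (low dose, high frequency): "defined as subjects who received a low dose (125 U or 200U) for 3 or 4 cycles".
- LDLF (low dose, low frequency): the corresponding definition for 1 or 2 low-dose cycles.

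It then sets a condition: "Subjects will appear in only one group, and TEAEs will be summarized for subjects in each group". Two sentences deal with subjects who had both dose levels: "Subjects who received a high dose for 2 cycles and a low dose for 2 cycles will be included in the HF group", and "Subjects who received a high dose for 1 cycle and a low dose for 1 cycle will be included in the HL group".

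SAP 3.6 explains why cumulative exposure matters here: "The sample size for this study is based on a requirement from Regulatory Authorities to collect safety data on approximately 350 subjects treated once", plus at least 100 subjects with 3 or 4 cycles at either dose level, "with at least 50 subjects treated with the high-dose DAXI for injection for 3 or 4 continuous treatment cycles". SAP 3.4 sets the maximum at four cycles. Protocol 7.1 makes each further treatment depend on the response to the one before.

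**The concern.** Each definition looks at one dose level and ignores cycles at the other. A subject who had both levels therefore satisfies one high-dose and one low-dose definition, which conflicts with the one-group condition. The two tie-breaks should resolve this, but they send subjects to HF and HL, which are not among the four groups or in the visible SAP glossary. They also cover only the even splits.

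The two parts of the text also appear to use different meanings of frequency. In the definitions it is the number of cycles at that dose. In the 2+2 tie-break, if HF means HDHF, it is the total number of cycles, because a subject with two high-dose cycles joins a group defined by three or four.

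HDHF is the only visible adverse-event grouping that corresponds to the requirement for at least 50 subjects at high dose for 3 or 4 cycles. Its denominator and percentages depend on a rule the SAP does not state. In an open-label study, that rule could end up being chosen with the event data in view.

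**Working it through.** The plan gives no figure to reproduce, because this is a classification rule. The check applies the printed definitions to every possible history.

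**Inputs.** The four definitions, the one-group condition and the two tie-breaks are from SAP 9.3. The maximum of four cycles is from SAP 3.4. Let h be the number of high-dose cycles (250 U or 300 U) and l the number of low-dose cycles (125 U or 200 U), with 1 ≤ h + l ≤ 4.

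**Number of combinations.** For t cycles in total there are t + 1 combinations: 2 + 3 + 4 + 5 = 14. Two at each total are single-dose: 2 × 4 = 8. Mixed: 14 − 8 = 6.

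**Literal definitions.** Any h ≥ 1 meets exactly one high-dose definition, and any l ≥ 1 meets exactly one low-dose definition. So all 8 single-dose combinations meet one definition and all 6 mixed combinations meet two.

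**Possible completions.** Four ways of completing the rule were applied to the mixed combinations:

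- A: majority dose (ties to high), frequency from total cycles.
- B: any high dose counts as high, frequency from total cycles.
- C: printed definitions, with the high-dose definition taking precedence.
- D: majority dose (ties to high), frequency from cycles at that dose.

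| High + low | Definitions met | Printed tie-break | A | B | C | D |
|---|---|---|---|---|---|---|
| 1 + 1 | HDLF, LDLF | HL | HDLF | HDLF | HDLF | HDLF |
| 2 + 1 | HDLF, LDLF | none | HDHF | HDHF | HDLF | HDLF |
| 1 + 2 | HDLF, LDLF | none | LDHF | HDHF | HDLF | LDLF |
| 3 + 1 | HDHF, LDLF | none | HDHF | HDHF | HDHF | HDHF |
| 2 + 2 | HDLF, LDLF | HF | HDHF | HDHF | HDLF | HDLF |
| 1 + 3 | HDLF, LDHF | none | LDHF | HDHF | HDLF | LDHF |

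**Results.**

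- Tie-breaks cover 2 of the 6 mixed combinations, both with undefined labels. The other 4 have no rule, and all 4 are histories of 3 or 4 cycles.
- Read literally, 2+1, 1+2 and 2+2 meet only low-frequency definitions, although these subjects had 3 or 4 cycles.
- 1+1 and 3+1 fall in the same group under all four completions. The other 4 change group.
- If HF is taken as HDHF, 2+2 is settled. 2+1, 1+2 and 1+3 stay open: a programmer could treat the tie-break as a single exception to C or D, or as evidence for A or B.
- By ordered sequence there are 2 + 4 + 8 + 16 = 30 histories: 8 single-dose, 2 + 6 = 8 with a tie-break, and 3 + 3 + 4 + 4 = 14 with no rule. All 14 are among the 8 + 16 = 24 sequences of 3 or 4 cycles.

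**Effect on HDHF.** Subjects with 3+0, 4+0 or 3+1 are in HDHF under every completion. Those with 2+1 or 2+2 are added under A and B, and those with 1+2 or 1+3 under B only. The size of HDHF can vary by the number of subjects in these four patterns. These are counts of patterns, not subjects, and the patterns need not be equally likely.

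**The case against.** The intent is largely recoverable. With at most four cycles, 1+1 and 2+2 are the only even splits, and these are exactly the two the SAP addresses. If HF and HL are shorthand for HDHF and HDLF, then 2+2 goes to high frequency, 1+1 to low frequency, and ties go to high dose. That suggests total cycles with majority dose, so the problem could be called loose drafting. The summaries are also additional and descriptive. The primary endpoints (SAP 4.1) and the nine listed TEAE tables are broken down by dose and cycle without these groups. The requirement of 100 needs only total cycles, and SAP 7.1 already summarises how many subjects were treated in each cycle. No visible text says that the requirement of 50 will be read from HDHF.

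Most of this stands and limits the scope. It does not remove the contradiction. The shorthand reading is an inference, and HF is the ending of both HDHF and LDHF. Even if it is accepted, the printed definitions still place 2+1 and 1+2 only in low-frequency groups, against the total-cycle logic attributed to the tie-break.

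A reader might also infer that contrasting high-frequency with low-frequency groups would make repeat dosing look safer, because subjects who stop early cannot reach a high-frequency group. The visible SAP plans no such contrast. That dependence is inherent in any grouping by cumulative exposure.

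Text immediately before these groups in SAP 9.3, and the detailed dosing rules, are blacked out. A clarification or a limit on dose changes could be there.

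**Conclusion.** The point holds as an internal contradiction in SAP 9.3. All 6 mixed-dose combinations out of 14 meet two definitions despite the one-group condition, two have tie-breaks to undefined labels, and four have no rule. The definitions and the 2+2 tie-break also appear to count different things, so relabelling alone does not repair the rule.

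The effect is limited to the additional dose-frequency TEAE summaries, chiefly the membership of HDHF and its match to the exposure requirement of at least 50. The primary endpoints and the TEAE tables by dose and cycle are unaffected, and single-dose subjects are classified without ambiguity. How many subjects are involved is unknown, because the documents give no rate of change between low and high dose. The tie-breaks and Protocol 7.1 suggest that such changes are expected.

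Two stronger readings go too far. One is that mixed-dose subjects cannot be placed: 1+1 and 3+1 land in the same group under every completion tried. The other is that the table covering 3 or 4 cycles will be wrong: it is under-specified, and whether it misleads depends on the rule adopted and the number of mixed histories. The conclusion assumes that the blacked-out text does not supply the missing rule.

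**What to change.** Before database lock, replace the four definitions and both tie-breaks with one exhaustive, mutually exclusive rule covering all 14 combinations. State explicitly whether frequency counts total cycles or cycles at that dose.

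One rule that fits the apparent intent of both tie-breaks is completion A: frequency from total cycles received (1 or 2 = LF, 3 or 4 = HF), and dose from the level received in the majority of cycles, with ties to high. Other exhaustive rules are defensible, but one has to be written down. Replace HF and HL with defined labels.

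Under this rule HDHF includes 2+1 and 2+2. Report separately, therefore, the number of subjects with 3 or 4 high-dose cycles, so that subjects with only two do not count toward the target of 50.

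The cost is one SAP paragraph and one derived variable. The separate count could be lower than the HDHF group size, by the number of subjects with 2+1 or 2+2.
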